10.5. Sample Size

A total sample size of 20 evaluable subjects per cohort was determined to balance the competing goals of assessing the primary objective while not exposing more subjects to an investigational decreased radiation procedure than is required. Historical data has shown that approximately 20% of subjects with standard radiation treatment show in-brain distant failure at 6 months. This trial is looking to see if decreased radiation will provide similar efficacy to the standard of care. There will be an interim analysis after the first cohort completes their 6 month scans. If less than 20% of the subjects have in-brain distant failure, then the second cohort will start.

With 20 evaluable subjects in a cohort, the 90% confidence interval around the proportion of subjects who are expected to have in-brain distant failure at 6 months would extend at most +/- 14.7%. Up to 25 subjects may be enrolled in each cohort. Although subjects who die before 6 months without confirmed in-brain distant failure would be replaced if possible, the following table will show the estimated confidence interval widths assuming the 20% proportion of subjects who may have in-brain distant failure at 6 months:

Number of Patients:	15	20	25
90% Confidence interval width:	17.0%	14.7%	13.2%

As stated in section 7.1.9, patients will not be considered evaluable if the sum total of radiotherapy interruptions exceeds 3 normally scheduled treatment days.

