10.8. Analysis of Primary Objectives

All analyses will be done by cohort. For the primary objective, the number of patients who have in-brain distant failure in the evaluable patients will be summarized and exact binomial 95% confidence intervals will be determined.

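### The planned precision of ±14.7 points is a 90% normal-approximation half-width at an assumed 20% rate; the exact 95% interval to be reported extends 23.7 points above a 20% result

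*Combined protocol and SAP*

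**What the plan says.** Section 10.5 sets "A total sample size of 20 evaluable subjects per cohort". It gives a historical rate in which "approximately 20% of subjects with standard radiation treatment show in-brain distant failure at 6 months". The precision statement begins "With 20 evaluable subjects in a cohort, the 90% confidence interval around the proportion of subjects" and says that the interval for "in-brain distant failure at 6 months would extend at most +/- 14.7" percent. A small table follows, "assuming the 20% proportion of subjects who may have in-brain distant failure at 6 months". Its row is headed "90% Confidence interval width" and reads 17.0%, 14.7% and 13.2% for 15, 20 and 25 patients. The range goes to 25 because "Up to 25 subjects may be enrolled in each cohort".

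Section 10.8, which governs the primary analysis, says that the number of failures among evaluable patients will be summarised and that "exact binomial 95% confidence intervals will be determined". No section states the precision expected from that interval.

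**The concern.** Sections 10.5 and 10.8 describe different intervals for the same endpoint. They differ in confidence level (90% against 95%) and apparently in method, because a symmetric ± figure cannot come from an exact binomial interval centred away from 50%. In addition, a half-width calculated at one assumed rate is worded as an upper bound, and the table row names a width while holding what look like half-widths.

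The plan has no hypothesis test and no power calculation, so this precision statement is the only quantitative support for 20 patients per cohort. The primary objective (section 2.1) is a failure rate below 20%, and section 10.5 speaks of efficacy similar to standard care. For both, the upper confidence limit carries the inference. A reader of section 10.5 would expect an observed 20% to come with an upper limit of about 20 + 14.7 = 34.7%. If the reported limit is materially higher, an ethics or monitoring committee is being told that the trial is more informative than it is.

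**Working it through.** **Inputs.** From section 10.5: n = 15, 20 and 25, assumed failure proportion p = 0.20, confidence level 90%. From section 10.8: exact binomial interval, 95%.

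**Step 1: reproduce the stated figures.** Wald 90% half-width = 1.645 × √(p(1 − p)/n), with p = 0.20:

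- n = 15: 1.645 × √(0.16/15) = 17.0 points
- n = 20: 1.645 × √(0.16/20) = 14.7 points
- n = 25: 1.645 × √(0.16/25) = 13.2 points

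All three table entries match. Other candidates at n = 20 do not: Wald 95% gives 17.5, Wilson 90% gives 14.3, Wald 90% at p = 0.5 gives 18.4, and the exact 90% interval at 4/20 has arms of 12.9 and 20.1. The entries are therefore half-widths. The full Wald widths would be twice as large: 34.0, 29.4 and 26.3 points.

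**Step 2: is 14.7 a maximum?** The same formula with n = 20 gives 15.9 points at p = 0.25, 16.9 at p = 0.30 and 18.4 at p = 0.50. The stated bound holds on this formula only for observed rates at or below 20%, or at or above 80%.

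**Step 3: the interval that will be reported.** The exact (Clopper-Pearson) 95% limits for x failures in n are the 0.025 quantile of Beta(x, n − x + 1) and the 0.975 quantile of Beta(x + 1, n − x). At an observed 20%:

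| n | x | Exact 95% limits | Lower arm | Upper arm | Stated ± (section 10.5) |
|---|---|---|---|---|---|
| 15 | 3 | 4.3% to 48.1% | 15.7 | 28.1 | 17.0 |
| 20 | 4 | 5.7% to 43.7% | 14.3 | 23.7 | 14.7 |
| 25 | 5 | 6.8% to 40.7% | 13.2 | 20.7 | 13.2 |

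At n = 20 the upper arm is 23.66/14.71 = 1.61 times the stated figure. Changing only the method (exact, still 90%) takes the upper arm from 14.7 to 20.1 points. Raising the level to 95% takes it to 23.7.

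**Step 4: other counts with n = 20.**

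| Failures | Wald 90% half-width | Exact 95% limits | Upper arm |
|---|---|---|---|
| 0 | 0.0 | 0% to 16.8% | 16.8 |
| 1 | 8.0 | 0.1% to 24.9% | 19.9 |
| 2 | 11.0 | 1.2% to 31.7% | 21.7 |
| 3 | 13.1 | 3.2% to 37.9% | 22.9 |
| 4 | 14.7 | 5.7% to 43.7% | 23.7 |
| 5 | 15.9 | 8.7% to 49.1% | 24.1 |
| 6 | 16.9 | 11.9% to 54.3% | 24.3 |
| 10 | 18.4 | 27.2% to 72.8% | 22.8 |

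The longest upper arm is 24.3 points, at 6/20. The upper arm exceeds 14.7 points at every count from 0/20 to 10/20. That range includes all the counts that would open the second cohort (0 to 3 of 20, section 10.11).

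**The case against.** The strongest defence is that nothing has been miscalculated: all three figures reproduce, the 20% assumption is disclosed for the table, and the ± sign shows that half-widths are meant. On the Wald formula the half-width does not exceed 14.7 points at any rate up to 20%, which covers every result that meets the objective. The counterexamples at 5/20 and above would miss the objective anyway. The decision rules in sections 10.3 and 10.11 use the observed proportion, so no decision depends on an interval, and the exact 95% interval will appear in the results regardless. Section 10.5 also justifies 20 patients as a balance against exposing more people than necessary, and the trial is labelled a pilot. Finally, section 3.1 defines the primary outcome as an actuarial rate, so the binomial interval may not be the last word.

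Much of this stands. The arithmetic is right, the decision rules are untouched, the lower arm at 4/20 (14.3 points) lies within the stated figure, and precision is the only numerical justification rather than the only one. Full exact widths should not be set against the stated half-widths; like for like at n = 20, the mean half-width is 19.0 points against 14.7.

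None of it rescues the statement. Reading the bound as limited to rates of 20% or less helps only for the Wald 90% interval. For the interval in section 10.8, the upper arm exceeds 14.7 points at every passing count. Pilot status makes precision more central, not less. The actuarial wording in section 3.1 needs reconciling with section 10.8, but section 10.8 is the stated primary analysis and a 90% Wald half-width does not describe it.

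**Conclusion.** The point holds. The precision in section 10.5 belongs to an interval that the trial does not plan to report. With 20 evaluable patients and 4 failures, the planned exact 95% interval is 5.7% to 43.7%. Its upper arm is 23.7 points rather than 14.7, about 61% longer, of which 5.4 points come from the method and 3.6 from the confidence level. The largest count that opens the second cohort, 3/20, still has an upper limit of 37.9%. The wording as a maximum is wrong for observed rates between 20% and 80% on the plan's own formula, and the table row is mislabelled.

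This rests on section 10.8 being the intended primary analysis and on the evaluable count being the binomial denominator. It is a fault in the stated justification and in consistency between sections. It does not alter the stopping rules or by itself call for a larger sample.

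**What to change.** Rewrite the precision paragraph and table in section 10.5 using the method of section 10.8:

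- State that with 20 evaluable patients and 4 failures (20%), the exact 95% interval is 5.7% to 43.7%.
- Replace the table row with exact 95% limits at an observed 20%: 4.3% to 48.1% (3/15), 5.7% to 43.7% (4/20) and 6.8% to 40.7% (5/25). Label it as confidence limits.
- Remove the wording that presents the figure as a maximum.
- Consider adding the limits for 3/20 (3.2% to 37.9%), the largest count that opens the second cohort.

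If a 90% level is really intended, use an exact 90% interval in both sections; at 4/20 it runs from 7.1% to 40.1%. If the actuarial definition in section 3.1 is later chosen as the primary estimator, section 10.8 and this statement must both be redone for that estimator.

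The cost is one paragraph and one table row. The stated precision becomes less favourable; sample size, conduct and decision rules stay the same.

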7.1.9. Radiation Therapy Interruptions

1. Radiotherapy will be continued without interruption if at all possible.
2. If the sum total of radiotherapy interruptions exceeds 3 normally scheduled treatment days, the treatment will be considered an unacceptable deviation from the protocol. This should be reported to the Principal Investigator and the patient will be considered inevaluable on final data analysis.

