10.4.3. Efficacy Population

The efficacy population comprises all subjects who have received at least one dose of radiation, and have been evaluated for the primary endpoint (the 6 month scan). This population will be used for efficacy analysis.

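### The efficacy population in 10.4.3 conflicts with the interruption exclusion in 7.1.9 and 10.5, so the denominator of the primary result and of the 20% go/no-go rule is not settled

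*Combined protocol and SAP*

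**What the plan says.** Two definitions decide who counts, and they differ.

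- **Efficacy population (10.4.3).** It contains "all subjects who have received at least one dose of radiation, and have been evaluated for the primary endpoint", meaning the 6-month scan, and is designated for efficacy analysis. Treatment interruption is not a criterion.
- **Interruption rule (7.1.9 and 10.5).** Once interruptions exceed 3 scheduled treatment days, 7.1.9 classes the course as an unacceptable deviation and adds that "the patient will be considered inevaluable on final data analysis". Section 10.5 repeats this, citing 7.1.9: "patients will not be considered evaluable if the sum total of radiotherapy interruptions exceeds 3 normally scheduled treatment days".

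The sections that use a denominator do not agree on one. Section 10.8 (primary analysis) and section 10.3 (stopping rule) both refer to evaluable patients or subjects. Evaluable is not among the three sets defined in 10.4 (enrolled, safety, efficacy). Section 10.11 states the same 20% interim rule over patients, without the qualifier.

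On size, 10.5 says: "A total sample size of 20 evaluable subjects per cohort was determined to balance the competing goals". It also says: "Up to 25 subjects may be enrolled in each cohort". Replacement is mentioned only for patients who die before 6 months without confirmed distant failure.

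**The concern.** A patient with four missed treatment days and a 6-month scan is in the efficacy population under 10.4.3 and not evaluable under 7.1.9 and 10.5. Two analysts following different sections would report different numerators and denominators from the same data.

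The exclusion also depends on something that happens during the 10-fraction (Cohort A) or 8-fraction (Cohort B) course, after treatment has begun. It applies whatever the cause of the interruption. If interruption is related to the risk of new lesions outside the boosted volume, the remaining patients are a selected group. No analysis that puts the interrupted patients back is described.

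At stake are the primary estimate in each cohort and the decision after Cohort A. Below 20% distant failure, Cohort B opens at the lower whole-brain dose level; at 20% or more, the study stops.

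**Working it through.** **Inputs from the documents:** 20 evaluable patients per cohort, at most 25 enrolled, planning failure rate 20% (10.5); continue if the observed rate is below 20%, stop otherwise (10.3, 10.11); exact binomial 95% interval (10.8). **Not in the documents, so assumed below:** how often patients exceed 3 interrupted days, and their failure risk.

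**1. The plan's own figure.** Half-width of a 90% interval = 1.645 × √(0.2 × 0.8 / n). For n = 15, 20 and 25 this gives 16.99, 14.71 and 13.16 points, matching the 17.0, 14.7 and 13.2 in 10.5. The planning figure is reproduced.

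**2. The rule at n = 20.** Continuing requires at most 3 failures. P(X ≤ 3) for X ~ Binomial(20, p):

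| True rate p | 10% | 15% | 20% | 25% | 30% |
|---|---|---|---|---|---|
| P(continue) | 0.867 | 0.648 | 0.411 | 0.225 | 0.107 |

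**3. Effect of excluding one scanned patient near the boundary.**

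| All scanned | Excluded patient | After exclusion |
|---|---|---|
| 4/20 = 20.0%, stop (exact 95% CI 5.7-43.7%) | failed | 3/19 = 15.8%, continue (3.4-39.6%) |
| 5/25 = 20.0%, stop | failed | 4/24 = 16.7%, continue |
| 4/21 = 19.0%, continue | did not fail | 4/20 = 20.0%, stop |

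The decision can change in either direction. With 20 scanned, a single exclusion changes it only when exactly 4 have failed and the excluded patient is one of them. P(X = 4) is 0.218 at a true 20% rate and 0.130 at 30%.

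**4. Illustration of selective exclusion (assumed rates).** Let the true rate be 30%, with a fraction a of failing and 5% of non-failing patients excluded. The expected observed rate is 0.3(1 − a) / [0.3(1 − a) + 0.7 × 0.95].

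- a = 0.20: 0.240 / (0.240 + 0.665) = 26.5%; overall exclusion 1 − 0.905 = 9.5%.
- a = 0.30: 0.210 / (0.210 + 0.665) = 24.0%; overall exclusion 1 − 0.875 = 12.5%.

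The chance of continuing, simulated with 400,000 cohorts per row:

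| Exclusion | Enrol up to 25 to reach 20 evaluable | Start with 20, no replacement |
|---|---|---|
| none | 0.107 | 0.107 |
| 20% of failing, 5% of non-failing | 0.18 | 0.25 |
| 30% of failing, 5% of non-failing | 0.26 | 0.35 |
| non-selective, 9.5% | 0.11 | 0.16 |
| non-selective, 12.5% | 0.11 | 0.17 |

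The last two rows separate two effects. Without replacement, part of the rise comes from the smaller cohort: 3 failures still pass at n = 16 to 19, and fewer patients remain in whom a fourth could occur. With replacement up to 25 that part disappears, and only selection moves the result.

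**5. Equal risk can also work against continuing.** With 22 scanned, a 20% failure rate in everyone and 5-15% interrupted, exclusion changes continue to stop in 4.0-9.0% of cohorts and stop to continue in 2.1-3.9%.

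**The case against.** The exclusion is prespecified, objective and cross-referenced. Sections 10.3 and 10.8 both use evaluable, so with 10.5 they can be read as one coherent per-protocol approach. In a non-randomised pilot of specific dose levels, a set limited to courses delivered broadly as planned is defensible. That stands as a reason to keep such an analysis. It does not remove the conflict with 10.4.3, which assigns efficacy analysis to a different set, or the missing definition in 10.4.

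A reader might infer that the exclusion lowers the observed failure rate and so favours the reduced dose. The documents do not support this as a fact. They give no interruption rate and no causes, and deterioration during treatment is not the same event as a new lesion outside the planning target volume. Patients who die without a 6-month scan are already outside 10.4.3, so the extra effect is confined to those who are scanned.

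A reader might also infer that one exclusion generally decides whether the trial continues, or that the chance of continuing at a true 30% rate would reach 25-35%. The former holds only at the boundary. The latter assumes that excluded patients are not replaced, although 10.5 sets its target in evaluable patients and leaves five further places. Even so, 10.5 states no replacement rule for interruptions, so neither case can be ruled out.

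Finally, 7.1.9 speaks of the final analysis. The exclusion reaches the interim decision only through 10.3 read with 10.5, and 10.11 leaves that open. It is also fair to say that 10.4.3 itself conditions on a later event, having the scan; adopting it does not remove every selection of that kind.

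**Conclusion.** The point holds as an unresolved conflict over the analysis set, made worse by an exclusion that depends on an event after treatment starts and may be informative. It leaves the denominator of the primary result, and of the decision to open Cohort B, open to choice.

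The direction is uncertain. Exclusion would favour continuing if interrupted patients fail more often. Under the assumed selective rates and a true 30% failure rate, the chance of continuing rises from 11% to about 18-26% with enrolment up to 25. It is 25-35% without replacement, and stays at about 11% when exclusion is non-selective and patients are replaced. These figures illustrate sensitivity and do not forecast what will happen in this trial. The boundary results (4/20 against 3/19, and 4/21 against 4/20) need no assumption about interruption rates, but matter only if the data fall there.

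**What to change.** Reconcile 7.1.9, 10.3, 10.4.3, 10.5, 10.8 and 10.11 on one analysis set, defined in 10.4 and named identically wherever it is used.

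- Use the 10.4.3 population, without the interruption exclusion, for the primary analysis and the interim decision.
- Remove the statements in 7.1.9 and 10.5 that such patients are not evaluable, and keep recording these interruptions as protocol deviations.
- Report the result without these patients, by cohort, as a per-protocol sensitivity analysis.

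The cost is wording in the listed sections and one extra table. The small downside is that a few patients with interrupted courses are counted in the main result. No treatment or interruption rule changes.

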10.6. Patient Characteristics and Significant Protocol Violations

Baseline subject characteristics will be tabulated, such as demographics (age, race, gender), and disease characteristics (KPS score). Significant protocol violations such as with respect to eligibility criteria and cohort will be tabulated.

10.7. Disposition

The reasons for patient treatment and study discontinuation will be summarized by cohort.

10.8. Analysis of Primary Objectives

All analyses will be done by cohort. For the primary objective, the number of patients who have in-brain distant failure in the evaluable patients will be summarized and exact binomial 95% confidence intervals will be determined.

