2.1. Primary Objective

Evaluate two de-escalated whole brain radiation dose levels (in the setting of simultaneous integrated boost to gross lesions) with respect to in-brain distant control for brain metastases, defined as an in-brain failure rate outside of the planning target volume at 6 months of < 20%.

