3. OUTCOME MEASURES

3.1. Primary Outcome Measure

In-brain distant failure, defined as an actuarial 6-month rate of new parenchymal lesions seen outside the planning target volume of any lesion that received SIB on any post-treatment MRI (in all 3 planes) by 6 months. Follow-up MRIs will be fused with the planning scan using our planning software for this assessment.

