10.3. Criteria for Stopping Study

An interim analysis is planned when the final patient in Cohort A finishes their six month assessment. If 20% or more of the evaluable subjects have in-brain distant failure at the 6 month time point, then the study will stop.

Additionally, there will be an early stopping rule in place. Each patient will be evaluated at 6 months for in-brain distant failure. If 4 patients out of the first 10 patients within each cohort have in-brain distant failure at 6 months, then the expected percent of patients would be double of what is expected (40% vs the expected 20%). This finding will prompt a re-assessment of treatment efficacy to determine if the cohort should continue.

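### The primary outcome is defined as an actuarial 6-month rate, but the analysis and the Cohort A go/no-go use a crude proportion, and the plan is unclear about which early deaths count in it

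*Combined protocol and SAP*

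**What the plan says.** **Definition.** Section 3.1: "In-brain distant failure, defined as an actuarial 6-month rate of new parenchymal lesions seen outside the planning target volume", on any post-treatment MRI by 6 months. Section 3.2 uses the same actuarial wording for treated lesion control and overall survival.

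**Threshold.** The 20% cut is in 2.1, 10.3, 10.5 and 10.11. Section 3.1 gives none.

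**Analysis.** Section 10.8: "the number of patients who have in-brain distant failure in the evaluable patients will be summarized and exact binomial 95% confidence intervals will be determined". Section 10.9 plans Kaplan-Meier, with 6- and 12-month estimates, for local control and overall survival only.

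**Decision.** Section 10.3: "If 20% or more of the evaluable subjects have in-brain distant failure at the 6 month time point, then the study will stop". Section 10.11 applies the same cut to the patients, without the word evaluable.

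**Who counts.** Section 10.4.3 limits the efficacy population to patients who received radiation and "have been evaluated for the primary endpoint (the 6 month scan"). Section 10.5 says that "subjects who die before 6 months without confirmed in-brain distant failure would be replaced if possible". It sets 20 evaluable and at most 25 enrolled per cohort. Sections 7.1.9 and 10.5 make patients with more than 3 interrupted treatment days inevaluable.

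**Timing.** Section 7.4 orders MRIs at 3, 6 and 12 months. The study calendar allows ±30 days at the 6-month visit.

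**The concern.** An actuarial rate uses the failure-free follow-up of patients who die or are lost early. A patient with a clear 3-month MRI who dies of systemic disease in month 5 contributes to the quantity in 3.1, but is dropped and, if possible, replaced in the analysis of 10.5 and 10.8.

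The wording is not loose. Section 1.1 labels a cited control figure as crude rather than actuarial, so the authors distinguish the two terms. Of the three outcomes defined as actuarial, only the primary one, which decides whether Cohort B opens, has no time-to-event estimate.

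There is a second gap. Section 10.5 replaces only deaths without confirmed failure, which implies that a patient who fails at month 3 and then dies still counts as a failure. Section 10.4.3, read literally, removes that patient because there was no 6-month scan. The crude rate is therefore not fully defined, and the choice could be made after the data are seen.

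**Working it through.** **1. The plan's own figure.** Section 10.5 gives 90% half-widths at a 20% rate. With 1.645 × √(0.2 × 0.8 / n):

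| n | Computed | Stated |
|---|---|---|
| 15 | 16.99% | 17.0% |
| 20 | 14.71% | 14.7% |
| 25 | 13.16% | 13.2% |

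All three reproduce, so the sample size reasoning rests on a crude binomial proportion without censoring.

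**2. The rule.** With 20 evaluable, the study goes on at 3 or fewer failures (15%) and stops at 4 or more (20%). If the count is binomial, the probability of going on is 64.8% at a true rate of 15%, 41.1% at 20% and 22.5% at 25%.

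**3. Average gap when deaths are independent of failure.** Assumptions: constant hazards, MRIs at months 3 and 6, a true actuarial rate of 20%, and 6-month mortality D. Month-3 failures are kept and failure-free deaths dropped, as 10.5 implies.

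- Failure by month 3: 1 − √0.8 = 0.1056. Failure in months 3 to 6: √0.8 − 0.8 = 0.0944.
- Failures seen: F = √(1 − D) × 0.1056 + (1 − D) × 0.0944.
- Crude rate: F / (F + (1 − D) × 0.8).
- Example, D = 20%: F = 0.0944 + 0.0755 = 0.1700, and 0.1700 / (0.1700 + 0.6400) = 21.0%.

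| Assumed D | Crude rate | Gap, points | P(go) at crude rate |
|---|---|---|---|
| 10% | 20.5% | 0.5 | 39.2% |
| 20% | 21.0% | 1.0 | 37.0% |
| 30% | 21.6% | 1.6 | 34.4% |
| 40% | 22.4% | 2.4 | 31.4% |

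The last column compares with 41.1% at a rate of 20%, taking 20 evaluable patients throughout.

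**4. The literal reading of 10.4.3.** If every counted patient needs the 6-month scan and deaths are independent of failure, the crude rate stays at 20%. If failure raises the risk of death, it falls below the actuarial rate. In a simulation with 30% 6-month mortality absent failure and a tripled death hazard after it, the crude rate is about 15% against a scan-based Kaplan-Meier rate of about 17%. P(go) at those two rates is about 65% and 54%.

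**5. One cohort within the plan's limits.** There are 25 treated patients: 2 fail on the 3-month MRI, 5 die failure-free between the scans, and 18 others are scanned at month 6, of whom 2 fail.

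| Estimate | Calculation | Result | Decision |
|---|---|---|---|
| Crude, month-3 failures kept | (2 + 2) / (2 + 18) | 20.0% | stop |
| Kaplan-Meier | 1 − (23/25)(16/18) | 18.2% | go |
| Cumulative incidence, death competing | 4/25 | 16.0% | go |
| Crude, literal 10.4.3, if both month-3 failures die before the 6-month scan | 2/18 | 11.1% | go |

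Kaplan-Meier stays at 18.2% whether or not those two patients die after failing. The crude rate moves from 20.0% to 11.1%.

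**The case against.** The strongest reply is that the decision sections agree on the type of quantity. The threshold is not in 3.1. Section 10.3 states a percentage of evaluable subjects, 10.11 a percentage of patients, and 10.5 presents the historical 20% as a share of subjects. A reader might infer that the protocol holds two rival decision rules. It does not: 3.1 contains no rule, and the mismatch is between an outcome definition and the analysis and decision built on it. That part of the reply stands.

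A reader might also infer that the crude rate is failure conditional on surviving to the 6-month scan, or that it is always too high. Neither is established. The first holds only on the literal reading of 10.4.3, which 10.5 contradicts, and the direction depends on which section is followed.

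A third tempting reading is that 3.1 calls for cumulative incidence with death as a competing event. It says actuarial and mentions no competing risk. Cumulative incidence would be a third quantity, each failure-free death would lower it, and nothing shows that the 20% benchmark is on that scale.

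The size objection is fair as well. The cohort in step 5 uses all five possible replacements and lands exactly on the cut. The documents give no 6-month mortality for this population, and 4.2 excludes an expected survival under 6 months. The exact 95% interval for 4/20 runs from 5.7% to 43.7%, far wider than the average gap. In a 20-patient pilot, sampling error dominates.

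None of this reconciles 3.1 with 10.8, or 10.4.3 with 10.5.

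**Conclusion.** The point holds. The primary outcome is defined on one scale, then analysed and acted on using another, and the set behind the crude proportion is contradictory. With no death or loss before 6 months the estimates coincide. The gap comes from early deaths, which 10.5 expects.

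The expected shift is modest: 0.5 to 2.4 points over an assumed 10% to 40% mortality with independent deaths, and possibly in the other direction under 10.4.3. It matters because the stop in 10.3 and 10.11 is worded as binding and one patient separates the outcomes. The documents do not show that the crude rate would usually reverse the decision. They do leave open a choice of patient set that could, so it should be settled before Cohort A results are read.

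**What to change.** - **10.8:** estimate the 6-month in-brain distant failure rate by Kaplan-Meier, as 3.1 defines it, with a 95% confidence interval, in all treated patients except those made inevaluable by 7.1.9. Censor patients without failure at their last MRI visit.
- **Timing:** count failures on any MRI up to and including the 6-month visit, assigned by scheduled visit, so that a scan inside the ±30-day window counts.
- **10.5:** keep patients who die early in the analysis set; replacements are added to them.
- **10.3 and 10.11:** state that the 20% comparison after Cohort A uses this estimate.
- **10.4.3:** reconcile it with 10.5, so that a failure on an earlier MRI counts even if no 6-month scan follows.
- **Supportive results:** report the crude evaluable proportion with its exact interval, and the cumulative incidence with death as a competing event.

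The cost is a change of wording in these sections and two further standard estimates from MRI and death dates that the trial collects. The downside is that the 10.5 precision table would then describe only the supportive proportion.
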